## 1. LIST OF ABBREVIATIONS

$\alpha$ 7nAChR	$\alpha$ 7 nicotinic acetylcholine receptor
A $\beta$ 42	amyloid beta 1-42
AD	Alzheimer's disease
AE	adverse event
ALT	alanine transaminase
ANOVA	analysis of variance
AST	aspartate transaminase
AUC	area under the curve
BMI	body mass index
BUN	blood urea nitrogen
CFR	Code of Federal Regulations
C max	maximum plasma concentration
CRF	case report form
CRO	contract research organization
DSMB/DMC	Data Safety Monitoring Board/Data Monitoring Committee
EC	ethics committee
ECG	electrocardiogram
EDTA	ethylenediaminetetraacetic acid
FDA	Federal Drug Association
FLNA	filamin A
GCP	good clinical practices
GGT	gamma glutamyl transpeptidase
GLP	good laboratory practice
HBsAg	hepatitis B surface antigen
HCV	hepatitis C virus
HIV	human immunodeficiency virus
hERG	human ether-a-go-go-related gene
ICH	International Council on Harmonisation of Technical Requirements for Registration of Pharmaceuticals for Human Use
IR	insulin receptor
IRB	independent review board
LDH	lactose dehydrogenase
LOQ	limit of quantitation
NMDA	N-methyl D-aspartate
NOAEL	no observable adverse effect level
OTC	over-the-counter
PHCG	placental human chorionic gonadotropin
PK	pharmacokinetics
PTI	Pain Therapeutics, Inc.
QS	quantity sufficient
RBC	red blood cell
SAD	single ascending dose
SAE	serious adverse event
T max	time to C max
WBC	white blood cell

## 2. INTRODUCTION

Pain Therapeutics Inc. (PTI) is developing PTI-125, a novel drug candidate designed to treat and slow the progression of Alzheimer's disease (AD). PTI-125 binds with femtomolar affinity to filamin A (FLNA), a scaffolding protein we recently demonstrated is critical to beta amyloid's toxicity. Beta amyloid1-42 (A $\beta$ 42) exerts its toxic effects by hijacking the  $\alpha$ 7-nicotinic acetylcholine receptor ( $\alpha$ 7nAChR) and signaling via this receptor to hyperphosphorylate tau. In addition to disrupting the normal functions of  $\alpha$ 7nAChR and tau protein, this toxic signaling leads to the signature tangles and plaques found in brains of AD patients. In two animal models and in postmortem human AD brain tissue, PTI-125 restored function of three receptors that are impaired in AD: the  $\alpha$ 7 nicotinic acetylcholine receptor ( $\alpha$ 7nAChR); the NMDA receptor; and the insulin receptor (IR). PTI-125 also reduced tau hyperphosphorylation, amyloid deposits, neurofibrillary tangles and inflammatory cytokine release. We therefore expect PTI-125 to improve memory and slow or halt AD progression, which are clear improvements over existing therapeutics. Both mouse models used a single efficacious dose equivalent to 20-22 mg/kg/day PTI-125 free base. The first mouse study administered twice daily i.p. injections of 10 mg/kg (equivalent to 60 mg/m^2) PTI-125. The second study delivered 22 mg/kg/day (equivalent to 66 mg/m^2) via drinking water.

A robust nonclinical ADME, safety pharmacology, and general and genetic toxicology program has been carried out with PTI-125. In vitro metabolic profiling showed minimal metabolism across several species and in man. PTI-125 was rapidly absorbed and eliminated in in vivo studies in rat and dog with nearly 100% oral bioavailability, a 2.67-h half-life in dog, dose proportional PK and no accumulation. Safety pharmacology studies showed no adverse effects on gross behavioral and physiological parameters in the Irwin test of CNS toxicity in rats, no adverse effects on respiratory rate, tidal volume or minute volume in the rat respiratory test, and no adverse effects on arterial blood pressure, heart rate and ECG parameters in the dog cardiovascular study. The in vitro hERG test for cardiotoxicity also indicated no adverse effect. A full battery of genotoxicity studies was conducted (in vitro bacterial Ames, in vitro chromosomal aberration, and in vivo rat micronucleus test) and were all negative. An in vitro specificity screen showed no significant activation or inhibition of a panel of 67 receptors, channels and transporters.

PTI-125 was tested in single dose and repeat dose oral general toxicity studies in rats and dogs. In a 28-day repeat dose oral general toxicity study followed by a 28-day drug-free recovery period in rats, with PTI-125 dose levels up to and including 1000 mg/kg/day (equivalent to 6,000 mg/m^2), toxicity was mainly characterized at 1000 mg/kg/day by a decrease in mean body weight which continued during the recovery period. A diffuse cellular hypertrophy of the liver was seen at 1000 mg/kg/day in males and females and was interpreted as an adaptive response to the test article. There were no other adverse effects and all biologically significant findings noted during the dosing period were resolved at the end of the 28-day recovery period. A no-observed-effect-level (NOEL) could not be determined and the no-observed-adverse-effect-level (NOAEL) was determined to be 500 mg/kg/day (equivalent to 3,000 mg/m^2).

A 28-day repeat dose oral general toxicity study in dogs, followed by a 28-day drug-free recovery period, with PTI-125 dose levels up to and including 200 mg/kg/day (equivalent

to 4,000 mg/m^2). Findings included slight muscle fasciculations in some animals at the high dose only, an increase in blood pressure in high dose females, and sporadic alterations in clinical chemistry profiles at the high dose. All observations resolved during the recovery period. An NOEL could not be determined and the NOAEL was determined to be 100 mg/kg/day (equivalent to 2,000 mg/m^2).

It should be noted that in a 7-day non-GLP dose-range finding study in dogs, convulsions (rated "slight") were observed in one of six animals administered 300 mg/kg/day on Day 2 and Day 3. On Day 4, this dose was reduced to 150 mg/kg/day, and the high dose, 1000 mg/kg/day, was reduced to 200 mg/kg/day. Convulsions were not observed in the 1000/200 mg/kg/day animals.

FDA Guidance for estimating the maximum safe starting dose in initial clinical trials was followed in determining the dose levels for this clinical trial. A safe human starting dose of 1/10th the human dose equivalent of the NOAEL in the most sensitive species (dog) was calculated as 330 mg. This first in human Phase I Single Ascending Dose (SAD) study will assess the safety and pharmacokinetics of PTI-125 solution at three single oral doses (50, 100 and 200 mg, equivalent to 31, 62, and 123 mg/m^2, respectively) in healthy normal volunteers.

### 3. STUDY OBJECTIVES

The objective of this study is to determine the safety and pharmacokinetics of PTI-125 following single-dose oral administration in healthy male and female normal volunteers, age 18 - 45.

### 4. SUMMARY OF STUDY DESIGN

This is a Phase I, single center, randomized, double-blind, placebo-controlled, SAD study of three escalating doses of PTI-125 in healthy male and female volunteers, 18-45 years of age. A total of twenty-four (24) subjects will be enrolled into the study in one of three dose cohorts. Each cohort will contain 8 subjects; six (6) subjects will receive PTI-125 and two (2) will receive placebo in each cohort. Three single ascending doses of PTI-125 oral solution (50, 100, and 200 mg) or placebo solution will be administered to respective cohorts.

The study includes a screening period (Day -28 to Day -1) and an inpatient treatment period (Day 0 through Day 4) and a follow-up visit (Day 7). Subjects will report to clinic the day before dosing and will be randomized to receive either a single dose of orally administered PTI-125 or placebo. Each dose will be administered following an overnight fast of 10 h.

For each dose level, dosing will be staggered such that 2 subjects (one active and one placebo) will be dosed prior to the rest of the group. After a minimum of 24 h and review of all 24-h safety assessments (ECG, brief physical, vital signs and laboratory

---

 Guidance for Industry: Estimating the Maximum Safe Starting Dose in Initial Clinical Trials for Therapeutics in Adult Healthy Volunteers. FDA, CDER, July 2005.

assessments) an independent Data Safety Monitoring Board/Data Monitoring Committee (DSMB/DMC) will determine whether the remaining 6 subjects will be dosed. If safety concerns are raised, 2 additional subjects (randomized according to the Rand schedule to maintain blinding) will be dosed followed by collection and review of the 24-hour safety assessments. The DSMB/DMC will determine after review if dosing will proceed for the remaining 4 subjects.

PK blood samples will be obtained prior to dosing and at specified intervals during the study (0-72 h post-dose). PK parameters will be calculated using non-compartmental analysis.

Blood draws for laboratory testing will be performed prior to dosing and at 24 h post-dose. After safety assessments of ECG, vital signs and a brief physical exam at 72 h, subjects will be discharged from the clinic and will return 7 days post-dose for a final safety assessment.

#### **4.1 STOPPING CRITERIA**

Dose escalation will be suspended or stopped if any of the following occur and are potentially related to administration of the study drug:

- Clinical signs or symptoms of moderate intensity or greater in two or more subjects
- A single clinical sign or symptom of severe intensity
- AST/ALT elevation greater than 3x upper limit of normal
- Bilirubin elevation greater than 2x upper limit of normal
- Creatinine elevation greater than 1.5x upper limit of normal
- Any significant laboratory finding, confirmed by repeat laboratory testing

The DSMB/DMC may subsequently recommend a second sentinel group to proceed with planned protocol dosing, or termination of the study.

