#### 7.1.2. *In-patient Period - Study Days 0-4*

**Note:** Study Day 1 is defined as the day of dosing for each dose cohort.

Subjects will check into the clinic at the designated time on Day 0, and will remain confined to the clinic until Study Day 4. Upon check-in, the following assessments will be conducted:

- Confirmation of inclusion/exclusion criteria
- Ethanol breath test
- Urine drug screen
- Urine Cotinine test
- Review of concomitant medications
- Orthostatic vital signs (blood pressure, temperature, pulse and respiratory rate after a 3-min sitting period followed by blood pressure and pulse after a 2-min stand period).
- Brief physical examination

Following a supervised fast for at least 10 h, subjects will be administered a single oral dose of study drug (or placebo) on Study Day 1.

The appropriate dosing syringe of PTI-125 or placebo (15 ml ORA-sweet SF mixed with 1, 2 or 4 ml pH 5.2, 0.3 M citric acid / citrate buffer) mixed with ORA-sweet SF for taste masking will be administered. Subjects will also consume water provided as a rinse of the dosing syringe, to ensure complete consumption of study drug.

No food will be allowed for 4 h post-dose. Water will be allowed as desired except for 1 h before and 1 h after dosing. At 4 h post-dose, subjects will be provided a standard lunch.

On the morning of Study Day 1, within 30 min prior to dosing, the following assessments will be conducted:

- Orthostatic vital signs (blood pressure, temperature, pulse and respiratory rate after a 3-min sitting period followed by blood pressure and pulse after a 2-min stand period).
- Review of concomitant medications
- Blood sample collection for baseline PK assessment (Sample Time=0)
- On Day 1, blood sample collection for laboratory testing prior to dosing (Time=0)
- ECG (Time=0)

After dose, the following assessments will be conducted:

- Orthostatic vital signs (blood pressure, temperature, pulse and respiratory rate after a 3-min sitting period followed by blood pressure and pulse after a 2-min stand period) at approximately 10 and 30 minutes, and 1, 2, 3, 4, 8, 12, 24, 36, 48 and 72 h post-dose.
- Blood samples will be drawn at 20, 40, and 60 min following dosing and at 2, 3, 4, 6, 8, 12, 24, 36, 48 and 72 h for PK assessments
- Adverse event monitoring
- Clinical laboratory tests at approximately 24 h post-dose
- Brief physical examination at approximately 24 and 72 h post-dose

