- ECG at approximately 30 min, and 1, 2, 3, 4, 8, 12, 24, 36, 48 and 72 h post-dose.

Should procedures occur at the same nominal timepoint collection of the PK assessment will take priority. All other procedures will be performed within a sufficient +/- window for logistical purposes.

All subjects will receive a standardized lunch 4 h post-dose. All subsequent meals will be served at standard meal times.

Clinic personnel will monitor the subjects for the occurrence of any adverse events until subjects are discharged from the clinic. Subjects will be discharged from the clinic upon investigator judgment after results of all safety assessments following the last dose have been reviewed.

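### Section 4.1's only automatic action is to halt dose escalation: it does not hold subjects released but not yet dosed at the current level, and at 200 mg no escalation step is left

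*Combined protocol and SAP*

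**What the plan says.** Section 4 describes three cohorts of 8 (6 active, 2 placebo) at 50, 100 and 200 mg. At each level "dosing will be staggered such that 2 subjects (one active and one placebo) will be dosed prior to the rest of the group". The timing of the next step is "After a minimum of 24 h and review of all 24-h safety assessments", and the DSMB/DMC then "will determine whether the remaining 6 subjects will be dosed". The following sentence reads: "If safety concerns are raised, 2 additional subjects (randomized according to the Rand schedule to maintain blinding) will be dosed". The board reviews that second pair before the last 4 are dosed.

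Section 4.1 opens its list of six criteria with "Dose escalation will be suspended or stopped if any of the following occur and are potentially related to administration of the study drug". It closes with "The DSMB/DMC may subsequently recommend a second sentinel group to proceed with planned protocol dosing, or termination of the study".

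Two general powers stand elsewhere. Section 11 lets the sponsor end the study whenever it chooses. Section 13 lets the investigator depart from the protocol without prior notice to protect subjects. Neither is tied to the criteria in 4.1. The protocol gives no dosing interval between released subjects, describes no further DSMB/DMC decision within a cohort once all 6 are released, and does not say which of Sections 4 and 4.1 governs when both apply.

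**The concern.** This is a first-in-human study, and 4.1 is its stopping rule. A pre-specified criterion should lead to a defined action that site staff can carry out without interpretation. The defined action here is on escalation, meaning the move to the next cohort. Subjects waiting for the same dose that caused the event are not mentioned, and in the last cohort there is no next dose to withhold.

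At stake is whether a subject could be dosed, in keeping with the text, after a stopping criterion has been met at that dose and before anyone has decided that dosing should go on. A second, smaller question is what follows a criterion met in a sentinel. Section 4 says that a second pair *will* be dosed when concerns are raised, while 4.1 says that the board *may* recommend one.

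**Working it through.** **1. Cohort counts.** Inputs are from Section 4. Total: 3 × (6 + 2) = 24, which reproduces the plan's figure. After the sentinel pair, 8 − 2 = 6 remain, of whom 6 − 1 = 5 are active and 2 − 1 = 1 is placebo. So 5/6 = 83% of the active doses at each level come after the sentinel step. All of them are held by Section 4 until the DSMB/DMC releases them, so the gap in 4.1 can matter only after release.

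**2. What the automatic action can reach.** Escalation steps left when a criterion is met:

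| Current level | Steps left |
|---|---|
| 50 mg | 2 |
| 100 mg | 1 |
| 200 mg | 0 |

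At 200 mg the automatic clause has nothing to act on. Termination is then available as a DSMB/DMC recommendation (4.1) or at the sponsor's discretion (Section 11).

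**3. When each criterion could be met after release.** Section 7.2.1 schedules post-dose laboratory tests at 24 h and on Day 7 only.

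| Criterion in 4.1 | Type | Earliest scheduled opportunity after release |
|---|---|---|
| Moderate or worse signs, two or more subjects | Clinical | Any time |
| One severe sign | Clinical | Any time |
| AST/ALT | Laboratory | Released subject: own 24-h test. Sentinel: Day 7 |
| Bilirubin | Laboratory | As above |
| Creatinine | Laboratory | As above |
| Other significant laboratory finding, confirmed on repeat | Laboratory | As above, plus the repeat |

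Four of the six are laboratory criteria. Barring unscheduled tests, they can arise while subjects are still undosed only if dosing of the released 6 is spread over more than about a day (a released subject's 24-h test), or runs up to a sentinel's Day 7 visit. The two clinical criteria can arise within hours, and one subject alone can meet only the severe-sign criterion.

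**4. How many subjects could be unprotected.** If *k* of the released 6 have been dosed when the criterion is met, 6 − *k* are undosed. The protocol does not give *k* or the spacing that would determine it. The bounds are assumptions, not estimates:

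- All 6 already dosed: 6 − 6 = 0.
- The first released subject, if active, has a severe related sign before the next is dosed: 6 − 1 = 5, of whom 5 − 1 = 4 are active.
- A sentinel has one between release and the next dose: 6 − 0 = 6, of whom 5 are active.

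**5. The two sections side by side.** A severe, potentially related sign in a sentinel is both a safety concern under Section 4 and a criterion under 4.1.

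| | Section 4 | Section 4.1 |
|---|---|---|
| Second pair | *will* be dosed | board *may* recommend it |
| Stopping | in the preceding sentence: the board decides whether the 6 are dosed | board *may* recommend termination |

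Any pair drawn from 5 active and 1 placebo contains 1 or 2 active subjects under either section. The sections differ in whether the pair is automatic or recommended. They do not differ in the exposure that a second pair brings.

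**The case against.** The best case for the plan is that 4.1 already implies a pause. It is headed as stopping criteria, and a second sentinel group that lets planned dosing proceed makes sense only if dosing has been interrupted. The only second pair described elsewhere is within a dose level. This is a fair reading of the intent, but the pause remains something that staff must infer.

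On Section 4, the sentence just before the second-pair sentence gives the DSMB/DMC the decision on the remaining 6, so a stopping option exists, and safety concerns may cover lesser events than the listed criteria. That stands, and it reduces this part to an ambiguity.

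The other safeguards are also real: the gate at every level, the powers in Sections 11 and 13, and a top dose of 200 mg against the calculated safe starting dose of 330 mg in Section 2 (200/330 = 61%). They lower the risk. Apart from the gate, however, which is spent on release, none is a defined response to a criterion.

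Three stronger readings are tempting and are not supported:

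- *Dosing could not be stopped, or a second pair would be compulsory.* The board's decision on the 6, its power to recommend termination and the sponsor's discretion all contradict this.
- *Section 4 adds 1 or 2 active exposures where 4.1 allows 0.* Section 4.1 itself permits a second sentinel group, so this does not compare like with like.
- *The sentinels' later ECGs and vital signs show a large unguarded period.* ECGs and vital signs do continue at 36, 48 and 72 h, for example "ECG at approximately 30 min, and 1, 2, 3, 4, 8, 12, 24, 36, 48 and 72 h post-dose". But no criterion in 4.1 names either, and they count only if a result is judged a clinical sign.

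**Conclusion.** The point holds, as a limited fault in the wording of a safety rule. Followed as written, a stopping criterion met after release places no automatic hold on undosed subjects at that level, and at 200 mg it produces no automatic action at all.

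The practical window is mainly a severe related sign, or moderate signs in two subjects, while some released subjects are undosed. A laboratory criterion enters only if dosing is spread over days. The number of subjects affected cannot be derived from the protocol: if all 6 are dosed close together, it may be 0. The timing argument assumes no unscheduled laboratory tests. The wording of Section 4 beside 4.1 is a secondary ambiguity. Sample size and planned analyses are unaffected.

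**What to change.** In Section 4.1, extend the opening clause so that it suspends or stops both further dosing at the current level and dose escalation when a criterion is met, pending DSMB/DMC review. This also gives the rule something to act on at 200 mg.

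In Section 4, state that when a 4.1 criterion is met, 4.1 governs, and that a second pair is then dosed only on the DSMB/DMC's recommendation.

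The cost is a protocol amendment with EC/IRB approval and a possible short pause in dosing when a criterion is met. No subjects or procedures are added.

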## **9.2. ADVERSE EVENTS - SEVERITY RATING**

The severity of each AE should be characterized and then classified into one of three clearly defined categories as follows:

- Mild - the AE does not interfere in a significant manner with the subject's normal functioning level. It may be an annoyance.
- Moderate - the AE produces some impairment of functioning, but is not hazardous to health. It is uncomfortable or an embarrassment.
- Severe - the AE produces significant impairment of functioning or incapacitation and is a definite hazard to the subject's health.

These three categories are based on the Investigator's clinical judgment, which in turn depends on consideration of various factors such as the subject's report, and the physician's observations. The severity of the AE should be recorded in the appropriate section of the Adverse Event CRF.

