#### 9.4. SERIOUS ADVERSE EVENTS AND UNEXPECTED ADVERSE EVENTS - DEFINITIONS

Any AE that suggests a significant hazard, contraindication, side effect or precaution is defined as a Serious Adverse Event (SAE). An SAE includes (but is not limited to) an experience occurring at any dose that results in any of the following outcomes:

- Death
- A life-threatening event (i.e., the subject is at immediate risk of death from the reaction as it occurs). "Life-threatening" does not include an event that, had it occurred in a more serious form, might have caused death. For example, drug-induced hepatitis that resolved without evidence of hepatic failure would not be considered life-threatening even though drug-induced hepatitis can be fatal.
- In-patient hospitalization (hospital admission, not an emergency room visit) or prolongation of existing hospitalization.
- A persistent or significant disability/incapacity (i.e., a substantial disruption of the subject's ability to carry out normal life functions).
- A congenital anomaly/birth defect.

In addition, medical and scientific judgment should be exercised in deciding whether other situations should be considered an SAE (i.e., important medical events that may not be immediately life-threatening or result in death, but may jeopardize the subject or may require medical or surgical intervention to prevent one of the other outcomes listed in the definition above). Examples of such medical events include (but are not limited to): allergic bronchospasm requiring intensive treatment in an emergency room or at home, blood dyscrasias or convulsions that do not result in in-patient hospitalization, or the development of drug dependency or drug abuse.

An **unexpected** AE is one for which the specificity or severity is not consistent with the current Investigator's Brochure. For example, hepatic necrosis would be

unexpected (by virtue of greater severity) if the Investigator's Brochure only listed elevated hepatic enzymes or hepatitis.

Similarly, cerebral thromboembolism and cerebral vasculitis would be unexpected (by virtue of greater specificity) if the Investigator's Brochure only listed cerebral vascular accidents.

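### Section 4.1 has no seriousness trigger, so a lone, potentially related, non-laboratory SAE graded below severe does not by rule suspend dose escalation unless the two-subject trigger is also met

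*Combined protocol and SAP*

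**What the plan says.** The stopping rule in Section 4.1 opens: "Dose escalation will be suspended or stopped if any of the following occur and are potentially related to administration of the study drug". Six bullets follow. Two are clinical: "Clinical signs or symptoms of moderate intensity or greater in two or more subjects" and "A single clinical sign or symptom of severe intensity". The other four concern AST/ALT, bilirubin, creatinine, and any other significant laboratory finding confirmed on repeat. After a trigger, "The DSMB/DMC may subsequently recommend a second sentinel group to proceed with planned protocol dosing, or termination of the study".

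Section 9.2 grades intensity by investigator judgment. A moderate event involves "some impairment of functioning, but is not hazardous to health". A severe event involves "significant impairment of functioning or incapacitation and is a definite hazard" to health.

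Section 9.4 defines seriousness separately. It lists five outcomes, among them "In-patient hospitalization (hospital admission, not an emergency room visit) or prolongation of existing hospitalization", and adds "important medical events that may not be immediately life-threatening or result in death, but may jeopardize the subject". It sets no minimum intensity grade.

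Section 4 staggers dosing at each dose level. One active and one placebo subject go first, and the DSMB/DMC reviews their 24-h safety assessments before deciding on the remaining six. Section 9.5 requires SAEs to be reported to the sponsor within 24 h.

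**The concern.** Intensity and seriousness are different scales, and Section 4.1 uses only the first. The result is uneven. One symptom-free creatinine value above 1.5 times the upper limit of normal, if potentially related, suspends escalation. One potentially related hospital admission graded moderate does not.

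At stake is a step from 50 to 100 mg, or from 100 to 200 mg, in a first-in-human study after a related serious event, with no written requirement to pause first. Other provisions allow a pause, but none compels one on the ground of an SAE.

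**Working it through.** The documents state no operating characteristic for the stopping rule, so there is no figure to reproduce. The check is a reading of the rule against the definitions.

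**1. Count the triggers.** 4 laboratory + 2 clinical + 0 on seriousness = 6.

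**2. Can an SAE be graded below severe?** Severe in Section 9.2 needs two things together: significant impairment or incapacitation, and a definite hazard. Section 9.4 needs neither if the event leads to admission, and the important-medical-event paragraph asks only whether the event may jeopardize the subject. An event that leads to admission for observation without marked impairment, or one that is hazardous without marked impairment, can thus be serious and not severe. The second kind fits neither grade cleanly, because moderate excludes hazard, so the investigator must choose.

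**3. Run such an event through Section 4.1** (one subject, potentially related, no laboratory finding, graded mild or moderate):
- two-subject trigger: not met by one subject;
- single severe sign or symptom: not met;
- AST/ALT, bilirubin, creatinine, other laboratory finding: not applicable.

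Triggers met: 0 of 6.

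**4. When does the two-subject trigger close the gap?** If the SAE is graded moderate, one other subject with a potentially related event of moderate or greater intensity completes the count. If it is graded mild, two others are needed. The rule does not restrict the count to one symptom, one cohort or active treatment. The documents give no rate for such events, so take an assumed chance q per other subject, equal and independent across subjects. Given one SAE graded moderate, the chance that the trigger stays unmet is (1 − q)^n, where n is the number of other subjects:

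| q (assumed) | n = 8 − 1 = 7, one cohort | n = 16 − 1 = 15, two cohorts |
|---|---|---|
| 2% | 0.98^7 = 0.868 | 0.98^15 = 0.739 |
| 5% | 0.95^7 = 0.698 | 0.95^15 = 0.463 |
| 10% | 0.90^7 = 0.478 | 0.90^15 = 0.206 |

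If the SAE is graded mild, the chance is (1 − q)^7 + 7q(1 − q)^6 within one cohort: 0.992, 0.956 and 0.850. These are illustrations, conditional on the SAE having occurred. They show that the two-subject trigger closes part of the gap and not all of it.

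**5. Who is affected?** Only the 50 and 100 mg cohorts precede an escalation: 2 × 6 = 12 active subjects. Of these, 2 × 5 = 10 are normally dosed after the sentinel pair. The 2 active sentinel subjects are covered by the DSMB/DMC review only for events within its 24-h data; a later SAE in either falls in the same gap.

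**6. What could follow?** The next dose level could open. Because dosing is staggered there too, one active and one placebo subject would be dosed before the DSMB/DMC decides on the other six. As Section 4 describes it, that review covers the pair's own 24-h assessments and does not expressly include SAEs from the earlier cohort.

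**7. Dose context (Section 2).** The calculated safe starting dose is 330 mg, and 330 / 200 = 1.65 times the top dose. The dog NOAEL is 2,000 mg/m², and 2,000 / 123 = 16.3 times the top dose.

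**The case against.** The strongest reply is that the protocol's own definitions nearly empty the gap. An event graded moderate must not be hazardous, and an investigator who thinks an event may jeopardize the subject can hardly certify that. Most SAEs would therefore be graded severe and would trigger Section 4.1. This stands, and it is why the point is narrow. It does not close the gap: admission is an outcome and not a grade, a possible jeopardy is weaker than a definite hazard, and severe also needs marked impairment.

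Second, subjects are confined from Day 0 to Day 4 with repeated ECGs and vital signs (Section 7.1.2), so a minor event could be observed in the unit without admission. This also stands. Admission after discharge and the important-medical-event route remain.

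Third, there are other safeguards: the mandatory sentinel review at each dose level, SAE reporting to the sponsor within 24 h (Section 9.5), sponsor termination at any time (Section 11), and the investigator's freedom to act to protect subjects (Section 13). They limit the harm. The sentinel review must take place, but its outcome is a matter of judgment, and none of these provisions requires escalation to stop because of an SAE. Committee procedures are not among the documents and might contain such a rule.

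Fourth, the fix keeps some judgment, because medical importance is itself judged. True, but the judgment would then address seriousness directly, and the outcome-based part needs little judgment.

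A reader might also point to the convulsions rated slight in one of six dogs (Section 2). They carry little weight here. That rating is not a Section 9.2 grade, and a human convulsion would ordinarily be graded severe. By the protocol's own dog conversion (100 mg/kg = 2,000 mg/m²), 300 mg/kg/day is 6,000 mg/m², and 6,000 / 123 is about 49 times the top human dose.

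**Conclusion.** The point holds in its narrow form. Section 4.1 does not require suspension after a lone, potentially related, non-laboratory SAE graded below severe, unless the two-subject trigger is also met, and no other section of the documents compels a pause in escalation for it. The change is worth making because it is cheap and repairs a stated first-in-human safety rule.

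Three stronger readings should be resisted:
- That serious events are generally unguarded. Section 9.2 implies that SAEs graded below severe are a minority, and the safeguards above remain.
- That a whole cohort could receive the doubled dose unchecked. Only one active subject could, before the next DSMB/DMC decision.
- That the percentages in the working measure the gap. They depend on an assumed q and give no rate for the SAE itself, which the documents do not supply.

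The conclusion assumes that Section 4.1 is applied as written, and that committee procedures not seen here do not already provide for the case. Confidence is medium.

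**What to change.** Add one bullet to Section 4.1, under the existing header that limits the list to potentially related events: *Any single adverse event, regardless of intensity, that meets one of the five listed outcomes or the important-medical-event paragraph of Section 9.4.* Escalation is then suspended pending DSMB/DMC review, a role that Section 4.1 already gives the committee after a trigger.

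Do not refer simply to any SAE under Section 9.4. Its opening sentence is broad enough to take in an event that merely suggests a side effect, so one mild related event could suspend escalation.

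Optionally, copy the DSMB/DMC on the 24-h SAE report if its procedures do not already provide for this.

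The cost is one bullet in a protocol amendment, with no new committee, visit, procedure or data item. The downside is an occasional extra pause for an event later judged unrelated.
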